# 2. RESEARCH PLAN

#### **Purpose of Study:**

Chronic exertional compartment syndrome (CECS) is a debilitating condition that causes elevation in compartment pressure, which can restrict patients from work and exercise. Typical treatment is to relieve compartment pressure though surgery. While surgery is effective for 66% of patients, it comes with increased risk and typically takes at least 8-13 weeks for full return to activity. One unproven alternative for pain relief is the use of botulinum toxin, a paralyzing agent. Botulinum toxin injections into the affected area in the lower extremities have been shown in limited trials to be a potentially cost effective way to relieve pain and return patients to full activity faster. Therefore, we will investigate the feasibility of a simple outpatient one time injection regimen for the treatment of CECS. We think botulinum toxin injections will be a potentially cost-effective, low-risk alternative to surgery in reducing pain and returning patients to full activity.

# Hypotheses, Research Questions, or Objectives:

In adult military patients with confirmed CECS by intramuscular pressure (IMP) needle measurements, botulinum toxin injections may be a non-inferior effective alternative to surgical fasciotomy in reduction of pain and ability to return to full activity. Therefore, the goals of this project are 1) To determine the long term efficacy of botulinum toxin injections in CECS. 2) Compared with current data and previous studies, is botulinum toxin injections non-inferior to current treatment regimens for overall pain control and return to full activity.

## Significance:

Currently, the only definitive treatment option for CECS is surgical fasciotomy. A simple outpatient procedure would save time, money, and potentially decrease recovery time and improve quality of life. An injection in place of surgery would also limit the chances of surgical complications and need for repeat surgical interventions.

## **Military Relevance:**

CECS comes at significant cost to the military in terms of medical rehabilitation, surgery, and time lost. Additionally, those suffering from CECS are often non-deployable and unable to fully participate in all necessary activities, thus requiring waivers to be retained in the military. By finding a cost effective alternative to fasciotomy, with limited side effects, we hope to bring treatment costs of CECS down and to also allow soldiers to return to full activity faster and without restriction.

## **Background and Review of Literature:**

The long term objective of this project is to validate botulinum toxin injections as a non-inferior treatment option for pain control and ability to return to full activity for adult military members suffering from lower extremity Chronic Exertional Compartment Syndrome (CECS), when compared to surgical fasciotomy. CECS is a debilitating disorder in which pressure in muscle compartments increases with exercise and resolves with rest. This causes pain, paresthesia, and inability to tolerate exercise. CECS mainly afflicts the lower extremities, below the knee, but upper extremity CECS has also been reported. CECS mainly affects young active adults. At risk groups include males, active duty military members, and athletes, both professional and recreational. 1,3,4,5

The current standard for definitive management and treatment of CECS is surgical fasciotomy. According to a 2016 systematic review, surgical intervention for CECS is successful in only 66% of those affected, with 13% of patients reporting complications from surgery, and 6% needing a repeat procedure. Definition of success varied across studies, but included patient satisfaction, lack of surgical revision, and full return to activity. Besides risks and complications, surgery also required a mean of 13 weeks to return to full activity when effective. A 2011 Cohort showed 81% overall patient satisfaction with the procedure, but noted best results from fasciotomy were young participants <23 years old, who underwent isolated anterior compartment release. Satisfaction was defined as being pain free or significantly improved on a 5 point pain scale, varying from pain free to worse. A smaller 2014 retrospective chart review of elite athletes with CECS showed fasciotomy was initially successful in 85% with a mean return to elite activity of 10.4 weeks. However, 30.8 % had a return of symptoms within the follow-up period.

Likewise, conservative treatment options yield mixed results. A systematic review in May of 2016 showed massage, gait changes, chemodenervation, and ultrasound-guided (USG) fascial fenestration had few adverse effects, but long term results and efficacy were unknown and unverified. Another newer therapy, minimal incision fasciotomy was effective for returning patients to previous level activity in 94% of patients after 36 months follow up in a prospective trial. Though improved final outcome from regular surgical intervention, average return to activity and return to sport was 8 and 13 weeks respectively. 

Military personnel comprise a specific patient population for whom outcomes and return to full duty is important for continued service and deployment. A 2014 military cohort found women, junior enlisted service members, and the Army soldier experienced the highest incidence of CECS. There was also an association between increasing age and CECS incidence. The study also found 78% of patients were free from medical discharge or revision after surgery at short-term to mid-term follow-up. However, 28% of service members were unable to return to full duty and 45% experienced incomplete relief of symptoms. In a similar United Kingdom military study, only 47% of subjects' symptoms improved after surgery. Additionally, a 2014 retrospective review of one United States tertiary military facility showed a return to full military duty in only 41% of patients who underwent elective fasciotomy for CECS. In that study, 78% of patients remained in the military and 71% reported satisfaction with the operative outcome.

Treatment of CECS with botulinum toxin injections has shown effective and long term relief in initial studies. An initial case series; from November 2013; showed that a single series of injections at the proximal and distal end of the affected muscle was effective in relieving pain and decreasing intramuscular pressure up to the 9 months of follow up in 94% of patients. Sixty-nine percent of those participants did have a decrease in strength, which did not affect overall motor function with treatment, but no other adverse effects. An additional 2016 case report showed effective pain and

paresthesia relief from CECS after 1 set of injections for a recreational female athlete. In this report, the patient's symptoms resolved within 1 week. More importantly, she was able to return to full recreational activity within 4 weeks, with no return of symptoms throughout the 14 months of follow up without any weakness or adverse effect. However; current studies regarding dosage and long term recovery are limited. This study aims to further investigate effectiveness of dose dependent botulinum toxin injections to relieve pain and discomfort of CECS, time to return to full activity, long term effects of this intervention, and prevention of surgical fasciotomy.

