#### a. Interventions and Observations:

If CECS is diagnosed by intramuscular pressure (IMP) elevation, patients will be offered Botulinum toxin injection regimen into the affected compartment or referral to orthopedic surgeon for a possible surgical fasciotomy. Patients will be provided information regarding both Botulinum toxin injections and fasciotomy. Patients will be allowed to discuss fasciotomy with a surgeon prior to making a decision to participate in the study, if desired. Potential side effects of Botulinum toxin injection include possible bleeding, pain, infection, general muscle weakness, muscular atrophy, flu-like symptoms, breathing and swallowing difficulties and death. Potential side effects of fasciotomy include surgical site pain, bleeding, recurrence of symptoms, scarring, muscle weakness, nerve damage, hematoma, need for repeat operation, infection, reactions to anesthesia (e.g. anaphylaxis), blood clot, muscle wasting (atrophy), and death. These will be explained to participants during the consent discussion.

For those diagnosed with CECS and desire Botulinum toxin injections, they will receive 2 injections per affected compartment. Up to 50 units of Botulinum toxin will be injected into the proximal and distal portions of the compartment for a maximum total dose of 100 units. A solution of 100 units of Botulinum toxin per 2 mL of normal saline will be used for all injections. Standard sterile technique will be followed. Insertion in to the correct compartment will be accomplished using general landmarks. The compartment will be separated into thirds measuring from the tibial plateau to the head of the calcaneus. Injections will be given at approximately 1/3 the distance from the tibial plateau for the proximal injection and 2/3 the distance from the tibial plateau for the distal injection. If the lateral or deep posterior compartment is affected, a total of 50 units Botulinum toxin will be given, 25 units per injection. If the anterior or superficial posterior compartment is affected, a total of 100 units Botulinum toxin will be given, 50 units per injection. Of note, CECS mainly affects the anterior and lateral compartments and is rarely seen in the superficial posterior or deep posterior areas.

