### 6. DATA ANALYSIS

## **Data Analysis:**

Head-to-head comparison of patients undergoing or who have undergone standard of care surgical fasciotomy and investigational Botulinum toxin injections will be analyzed. Measures addressed will be pain severity, return to full activity, Lower Extremity Function index, and patient satisfaction over the course of pre-treatment, post-treatment, and 1, 3, 6 month follow-up visits.

A power analysis, shown below, was completed for this pilot study. Assuming equal sample sizes of groups, 2-tail alpha of .05, power=.8, and 67% of fasciotomy group will have no pain (i.e. pain < 3).4

- 1. 75% of injection group, no pain n=1008 total
- 2. 80% of injection group, no pain n=360 total
- 3. 85% of injection group, no pain n=176 total
- 4. 90% of injection group, no pain n=98 total
- 5. 95% of injection group, no pain n=60 total

As CECS is an infrequent diagnosis, this pilot study will have difficulty over the course of the year to obtain enough sample size for statistical significance. However, the hope is to obtain a promising trend and eventually expand the study to obtain significance pending initial results.

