# **Outcome Measures:**

For the prospective portion of the study, the primary outcome will be pain reduction from either a standard of care surgical fasciotomy or an investigational Botulinum toxin treatment regimen. Adequate pain reduction will be rated as less than 3 on the universal pain scale. Secondary outcomes will include return to full activity and patient satisfaction. Full activity is defined as being able to run 1.5 miles and complete work duties with either no pain or pain that can be ignored. To assess patient satisfaction, patients will be asked if they were or were not satisfied with their surgical fasciotomy or their Botulinum toxin injections during their 6 month follow-up visit.

For the retrospective portion of the study, the same measures will be addressed for subjects who have undergone a standard of care surgical fasciotomy, but only on a pre- and post-treatment basis.

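### The injection is expected to be low-risk, but no adverse event, weakness, complication or later procedure is planned as an outcome in any group

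*Combined protocol and SAP*

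**What the plan says.** Relative safety is part of the case for the study. The Purpose of Study expects a "potentially cost-effective, low-risk alternative to surgery in reducing pain and returning patients to full activity". Military Relevance speaks of "By finding a cost effective alternative to fasciotomy, with limited side effects". Significance argues that replacing surgery would avoid surgical complications and repeat operations. The Background closes by naming, among the aims, the treatment's long-term effects and the avoidance of fasciotomy.

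The formal hypothesis is narrower: "botulinum toxin injections may be a non-inferior effective alternative to surgical fasciotomy in reduction of pain and ability to return to full activity".

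The Background gives harm figures for both treatments. For a 2013 injection series: "Sixty-nine percent of those participants did have a decrease in strength". The same sentence adds that overall motor function was not affected and that there were no other adverse effects. A 2016 case report is described as free of weakness and adverse effects. For fasciotomy, a 2016 systematic review is cited for 13% complications and 6% repeat procedures.

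Interventions and Observations lists the toxin's possible effects for the consent discussion, including "general muscle weakness, muscular atrophy, flu-like symptoms, breathing and swallowing difficulties and death", and gives a similar list for fasciotomy. The Risks section repeats both lists.

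Data Analysis states: "Measures addressed will be pain severity, return to full activity, Lower Extremity Function index, and patient satisfaction". Outcome Measures states: "Secondary outcomes will include return to full activity and patient satisfaction".

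**The concern.** The plan cites harm rates for both treatments, tells patients about the harms, and plans to record none of them as an outcome. If it is followed exactly, the report can describe pain, function, activity and satisfaction, but has no planned data on what either treatment cost the patient in complications, weakness or a further operation. An injected patient who later has a fasciotomy is not captured by any listed item, although avoiding fasciotomy is a stated aim.

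The plan hopes to expand the study if early results are promising. That decision would be taken with no planned description of harm. Transient weakness that is not asked about at the time can be recovered afterwards only by recall.

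**Working it through.** **1. What each section collects.**

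- Research Design and Methods, both groups: demographics, time to diagnosis, minutes of exercise to symptoms, minutes of rest to relief, LEFI and pain, plus satisfaction at six months.
- Interventions and Observations: LEFI and pain scale at 1, 3 and 6 months; activity and satisfaction as secondary outcomes.
- Procedures table under Source of Research Material: X-rays and blood samples, compartment pressures, LEFI, pain scale, satisfaction survey, pregnancy test.
- Data Analysis, Outcome Measures and Statistical Analysis: pain, return to activity or duty, LEFI, satisfaction.
- Retrospective fasciotomy patients (Outcome Measures): the same measures, before and after treatment only.

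Items on adverse events, weakness, complications or later procedures: none, in any group.

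**2. The plan's own calculation.** The power table concerns pain only. With the pooled-variance formula for two proportions and no continuity correction,

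n per group = [1.960·√(2p̄(1−p̄)) + 0.842·√(p₁(1−p₁)+p₂(1−p₂))]² / (p₁−p₂)², with p₁ = 0.67,

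the totals for 75, 80, 85, 90 and 95% are 1008, 360, 176, 98 and 60, matching all five rows. Nothing below depends on that table. It shows only that no precision was considered for harms.

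**3. Precision if harms were collected.** Sample Size Estimation gives 15 for the prospective portion, which Research Design and Methods describes as holding both an injection arm and a fasciotomy arm. The number injected is not stated. I assume a range of 5 to 15, with 15 as the ceiling.

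- Exact (Clopper-Pearson) two-sided 95% upper limit with zero events: 1 − 0.025^(1/n).
- Chance of at least one event at true rate p: 1 − (1−p)^n.

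| Injected (assumed) | Upper limit, 0 events | Count near 69%, exact 95% CI | P(≥1) at 69% | P(≥1) at 13% | P(≥1) at 6% |
|---|---|---|---|---|---|
| 5 | 52% | 3/5: 15% to 95% | 99.7% | 50% | 27% |
| 8 | 37% | 6/8: 35% to 97% | >99.9% | 67% | 39% |
| 10 | 31% | 7/10: 35% to 93% | >99.9% | 75% | 46% |
| 15 | 22% | 10/15: 38% to 88% | >99.9% | 88% | 60% |

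The 69, 13 and 6% are literature figures given without counts. They serve here only as plausible event rates.

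**4. Reading the table.** An event as common as 69% would almost certainly be seen with only five injected patients, so leaving it out loses information the pilot could have supplied. For an uncommon event, even complete collection with none observed leaves rates up to at least 22% compatible with the data.

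**5. Formal comparison.** Suppose the arms split 8 and 7, with 13% of surgical and an assumed 1% of injected patients having an event. Fisher's exact test at two-sided 5% then has power of about 0.7%. Description with intervals is the realistic aim.

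**The case against.** Several points on the other side stand and limit the finding.

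- *A reader might infer that the study tests a safety claim.* It does not. Low risk is an expectation in the Purpose; the hypothesis and both goals concern pain, efficacy and return to activity.
- *A reader might take the 69% as contradicting the low-risk expectation.* The same sentence says motor function was unaffected and nothing else adverse occurred, and the case report found no weakness. The figure shows that weakness is expected and countable. It does not show that the injection is harmful.
- *A reader might say that nothing relevant is collected.* LEFI at baseline and three follow-ups, and the 1.5-mile run with work duties, could reflect disabling weakness. This is partial: neither measure identifies weakness as the cause, and neither records infection, nerve injury, systemic toxin effects or a further operation.
- *A reader might take the not-applicable entry for Data Safety Monitoring to mean that events go unrecorded.* The entry refers to a list that is not in the supplied text, so it cannot carry that meaning. The consent form, investigational drug form, FDA letter and satisfaction survey are also attachments not supplied, and reporting rules may be there. Even so, no safety outcome appears in the sections that define what is analysed.
- *A reader might set the 22% limit against the 13% surgical complication rate.* The first bounds one type of event and assumes all 15 are injected; the second counts complications overall. The two are not comparable.

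**Conclusion.** The point holds as a gap between what the plan expects and what it plans to measure. No harm outcome is named for either prospective arm or for the retrospective group, so statements about low risk, limited side effects or avoided fasciotomy would have no planned data behind them. The documents do not support saying that the study tests safety, that its sources contradict the low-risk view, or that adverse events will go unreported.

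On size, the zero-event upper limit runs from 52% (5 injected) through 37% (8) to 22% (15). Collecting harms would allow common events to be described, but would not by itself establish low risk. This rests on the assumed range for the number injected and on the supplied text alone. The primary pain analysis is unaffected. It is an inexpensive improvement that should be made before enrolment, because events not asked about at the time are hard to recover.

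**What to change.** 1. Add adverse events and complications as a named, descriptive secondary outcome.
2. At the existing 1, 3 and 6 month contacts, give both prospective arms the same fixed yes/no checklist. Build it from the effects already listed in Interventions and Observations and in Risks, including self-reported weakness and any repeat or subsequent fasciotomy.
3. For consenting retrospective patients, abstract complications and repeat procedures from the medical record. Report these separately, and neither pool nor contrast them with the prospective answers. Solicited events are found more readily than charted ones, so a contrast would tend to count against the injection.
4. State the number in each group. Report n/N with exact 95% confidence intervals per group and no hypothesis test.
5. Limit any conclusion about low risk or limited side effects to what those intervals support.

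The cost is a one-page checklist taking a few minutes per contact, modest chart abstraction and one table. No extra patients or clinical procedures are needed. The limitation is that self-reported weakness cannot be compared with the cited 69%, because the protocol does not say how strength was measured in that series.

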For those diagnosed with CECS and desire surgical fasciotomy, the team will discuss the fasciotomy procedure and risks as mentioned above. For the procedure, the patient will be placed under general anesthesia and then linear incisions will be made into the affected compartment releasing the underlying fascial layer, reducing the pressure of the compartment. The entire procedure will be accomplished in a sterile fashion. Further details and scheduling will be per the orthopedic surgeon's recommendations.

After the initial Botulinum toxin injection regimen or fasciotomy, patients will be assessed at 1 month, 3 months, and 6 months with the LEFI and universal pain scale. Primary outcome will be pain reduction. Adequate pain reduction will be rated as less than 3 on the universal pain scale. Secondary outcomes will include return to full activity and patient satisfaction. Full activity is defined as able to run 1.5 miles and complete work duties with either no pain or pain that can be ignored. To assess patient satisfaction, patients will be asked if they were or were not satisfied with the Botulinum toxin injections at the 6 month visit.

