### **Statistical Analysis:**

The primary measure to be analyzed will be comparing pre- and post-treatment pain for each of the two treatment regimens using the universal pain scale. Additionally, participants will be evaluated for return to duty, overall patient satisfaction, and the Lower Extremity Functional Index will be compared pre- and post-treatment. The study team will complete the statistical analysis.

Number of Subjects:				
	# Planned to Enroll	# Enrolled	# Planned to Complete Study	TOTAL

Number of Subjects at Scott AFB	15	0	15	15
---------------------------------	----	---	----	----

Number of Data Records Entered into the Study:					
	# Planned to Enroll	# Enrolled	# Planned to Complete Study	TOTAL	
Number of Subjects at Scott AFB	10	0	10	10	

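### Time to return to full activity is a stated aim, but no return date is planned: timing is known at best to the visit interval in prospective patients and not at all below 6 months in the retrospective fasciotomy group

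*Combined protocol and SAP*

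**What the plan says.** **Aim and rationale.** The last sentence of Background and Review of Literature lists "time to return to full activity" among the things the study will investigate. Purpose of Study describes injection as a possible way to "relieve pain and return patients to full activity faster", and Military Relevance repeats the hope of a faster return. The benchmarks are given in weeks. For surgery they are 8-13 weeks (Purpose of Study), a mean of 13 weeks (systematic review), a mean of 10.4 weeks (elite athletes) and, for minimal incision fasciotomy, "average return to activity and return to sport was 8 and 13 weeks respectively". For injection, one case report describes full recreational activity within 4 weeks.

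**Outcome and schedule.** Sections 3a and 6 (Outcome Measures) define full activity as a state: a 1.5-mile run and work duties with pain absent or ignorable. The definition has no time element. Section 3a says that "patients will be assessed at 1 month, 3 months, and 6 months with the LEFI and universal pain scale". Data Analysis lists return to full activity among measures followed "over the course of pre-treatment, post-treatment, and 1, 3, 6 month follow-up visits".

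**Data items.** The clinical data list in Research Design and Methods and the procedures table under Source of Research Material name the LEFI, the pain scale and the satisfaction survey. Neither names a return date or a return-to-activity item.

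**Retrospective group.** These patients recall their state before surgery and six months after it. Outcome Measures confirms that the same measures apply, "but only on a pre- and post-treatment basis".

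**Analysis.** Statistical Analysis says "participants will be evaluated for return to duty", a term it does not define, and describes no time-based method.

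**The concern.** An aim about time needs a measured time. The plan defines a state, to be checked on three occasions in prospective patients and on one post-treatment occasion in retrospective patients, and it lists no form item to record even that state. If the plan is followed as written, the team will not be able to say how many weeks either treatment took. With 15 prospective and 10 retrospective patients expected, losing timing information that a single question could supply is an avoidable waste. The retrospective group is the weaker part: a patient back at full activity in week 4 and one back in week 24 would be recorded alike.

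**Working it through.** **1. The plan's own figures.** The documents contain no calculation for return to activity. The only one is the power table for pain below 3 (67% against 75, 80, 85, 90 and 95%; two-sided alpha 0.05; power 0.8). Its totals of 1008, 360, 176, 98 and 60 reproduce exactly with the pooled-variance two-proportion formula without continuity correction. They have no bearing on this point.

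**2. Visit times in weeks.** One month = 365.25 / 12 / 7 = 4.35 weeks. The visits therefore fall at:
- 1 month: 4.35 weeks
- 3 months: 3 x 4.348 = 13.04 weeks
- 6 months: 6 x 4.348 = 26.09 weeks

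The gap between the first two visits is 13.04 - 4.35 = 8.7 weeks.

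**3. Which visit first detects each benchmark.**
- 4 weeks (injection case report): the 1-month visit, with 4.35 - 4 = 0.35 weeks to spare.
- 8, 10.4 and 13 weeks (surgery): all at the 3-month visit. The 13-week value has only 13.04 - 13 = 0.04 weeks to spare.

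The schedule therefore separates the documents' injection figure from their surgical figures, but by narrow margins. No visit windows are stated. A 1-month visit held three days early (0.43 weeks) would miss a 4-week return, and a 3-month visit held one day early (0.14 weeks) would miss a 13-week return.

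**4. What interval data can do at group level.** The following inputs are assumptions that are not in the documents: the 15 prospective patients split 8 v 7, every patient eventually returns, return times are lognormal with coefficient of variation (CV) 0.1 to 0.8, visits fall exactly on schedule, and return status is recorded at each visit. Each power comes from 1,000 simulated trials with a rank test at two-sided 0.05, applied either to exact dates or to the visit interval. The 5-week mean is an illustration and appears nowhere in the documents.

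| Mean weeks | Data used | CV 0.1 | CV 0.3 | CV 0.5 | CV 0.8 |
|---|---|---|---|---|---|
| 4 v 13 | dates | 100% | 100% | 99% | 79% |
| 4 v 13 | visits only | 100% | 99% | 94% | 68% |
| 4 v 10.4 | dates | 100% | 100% | 91% | 61% |
| 4 v 10.4 | visits only | 99% | 94% | 82% | 54% |
| 5 v 13 | dates | 100% | 100% | 92% | 64% |
| 5 v 13 | visits only | 58% | 82% | 80% | 58% |
| 5 v 8 | dates | 100% | 75% | 38% | 18% |
| 5 v 8 | visits only | 1% | 29% | 23% | 15% |

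A Fisher test on the proportion returned at 1 month has power of 95, 74, 69 and 56% for 4 v 13 weeks across the same CVs. Visit data therefore keep much of the information when the two means lie on either side of a visit. They lose much of it when both means lie between the same two visits and the spread is small.

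**5. Retrospective group.** There is one post-treatment time point, at 6 months (26.09 weeks). Every return before it is recorded identically, so the 10 patients contribute at most returned or not by 6 months.

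**The case against.** A reader might infer that the claim of faster return cannot be tested at all. The documents do not support that. Data Analysis places return to full activity at the 1, 3 and 6 month visits, and the prospective design includes both treatments. Two patients sharing an interval does not prevent a comparison of groups, and under the assumptions above visit data alone detect the documents' contrasts of 4 against 10.4 or 13 weeks with 54 to 100% power.

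That rescue is conditional, however. It needs a return-status item, which the data lists do not name; a named analysis, which the plan lacks; and enough prospective surgical patients. The split of the 15 is not stated, and the Dates section describes the prospective timeframe only for injection patients. If few choose surgery, the comparison falls back on the retrospective group, which has no timing.

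A reader might also take speed to be a formal objective. It is not. The numbered goals concern long-term efficacy and non-inferiority in pain control and return to full activity; return to full activity is a secondary outcome; and the pilot openly seeks a trend. This limits the weight of the point but does not remove the aim stated in Background.

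Finally, the survey forms are attachments that were not available. It can be said that no date item is listed, not that the forms contain none.

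**Conclusion.** The point holds as an inexpensive improvement to a secondary aim, not as a flaw that defeats the study. Time to return is an aim without a planned measurement. In prospective patients it is known at best to intervals ending at about 4.3, 13.0 and 26.1 weeks, which supports only a coarse comparison. In the 10 retrospective patients nothing below 6 months is planned, so speed cannot be compared with them.

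For prospective patients, recording dates raises power modestly for 4 v 13 weeks (at CV 0.8, from 68% to 79%) and more for contrasts inside one interval (5 v 8 weeks at CV 0.3, from 29% to 75%). It does not rescue small contrasts with wide spread (5 v 8 weeks at CV 0.8: 15% to 18%). These figures rest on the assumed 8 v 7 split, lognormal times and universal return. The statements about visit intervals and the retrospective group rest on the documents alone.

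**What to change.** - First check the attached forms for an existing date item.
- If there is none, add a short question at the 1, 3 and 6 month contacts: has full activity, as defined under Outcome Measures, been met, and on what date (or in which week) was it first met?
- Ask the same in the retrospective survey, and check the answer against any duty-release date in the medical record.
- Summarise time from treatment to return by arm with a Kaplan-Meier curve and 95% confidence interval, censoring patients not returned at 6 months. Report the median only if it is reached: one military series cited in Background had 41% returning to full duty after fasciotomy, which is below half.
- Add the proportions returned at 1 and 3 months for prospective patients, and treat the retrospective dates as descriptive.
- In Statistical Analysis, replace return to duty with the defined return to full activity.

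The cost is a short question and a wording amendment; no treatment or visit changes. The downside is recall error. In prospective patients recall reaches back no further than the previous contact. In retrospective patients it may be substantial: the timing of their contact is not stated, and if it ran to the end of prospective collection, the oldest operation (July 2016) would lie 3 years 9 months before April 2020.
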